2.2 Analysis sets

The following analysis data sets will be used in the analyses:

Randomized Set (RS): The RS will consist of all randomized patients.

Full Analysis Set (FAS): The FAS will consist of all randomized patients with the exception for those patients who have not been qualified for randomization and have not received study treatment, but have been inadvertently randomized into the study. Following the intent-to-treat principle, patients will be analyzed according to the treatment to which they were assigned at randomization. Efficacy variables will be analyzed based on the FAS as the primary set.

Safety Set (SS): The SS will consist of all randomized patients who have received at least one dose of study treatment. Patients will be included in the analysis according to the treatment actually received. The SS will be used for the analyses of safety variables.

Per-Protocol Set (PPS): The PPS will be a subset of the FAS, which will consist of the patients who do not have major deviations from the protocol procedures. Major protocol deviations will be pre-specified prior to unblinding treatment code for analysis. This supplemental analysis set will be used to support the primary analysis results.

2.2.1 Subgroup of interest

The following subgroups will be analyzed for the primary objective and the secondary objective for AEs of special interest:

- 1. Age group (<65, ≥ 65 years) and (<75, ≥ 75 years)
- Ejection fraction categories prior to randomization (>40%, >30% 40%, >20% 30%, ≤20%)
- 3. Prior use of ACEi/ARB (at the time of hospitalization)
- 4. Baseline quartiles of NTproBNP (randomization sample)
- 5. Baseline eGFR (<45, 45 <60, ≥ 60 ml/min/1.73 m²)
- 6. Systolic blood pressure at randomization ($<110, \ge 110 \text{ mm Hg}$)

See Sections 2.5 and 2.7 for further details on the primary and secondary objectives, respectively.

2.3 Patient disposition, demographics and other baseline characteristics

2.3.1 Patient disposition

All patients will be used for the summary of patient disposition. The following categories will be summarized:

- Number of patients who were screened
- Primary reason for not continuing to double-blind phase

- Investigator decision
- Subject/Guardian decision
- Screen failure
- Adverse event
- o Pregnancy
- Study terminated by sponsor
- Technical problems
- o Death
- Number of patients who were randomized
- Number and percentage of patients who were treated
- Number and percentage of patients who prematurely discontinued study treatment during double-blind phase
- Number and percentage of patients who prematurely discontinued study treatment during double-blind phase, excluding deaths
- Number and percentage of patients who prematurely discontinued study treatment during open-label phase
- Number and percentage of patients who prematurely discontinued study treatment during open-label phase, excluding deaths
- Reasons for premature discontinuation of study treatment (separately for double-blind phase and open-label phase)
 - o Adverse event
 - o Death
 - Protocol deviation
 - Investigator decision
 - Subject/Guardian decision
 - Lost to follow-up
 - Technical problems
 - o Pregnancy
 - Withdrawal of consent
 - Noncompliance with study treatment
 - Study terminated by sponsor
- Study duration in months [(date of last contact/death date of randomization +1)/30.3475]

A separate summary for study completion will be presented and the FAS will be used. The following categories will be summarized at Week 8 by treatment group, open-label and pooled sacubitril/valsartan:

- Patients who received at least one dose of study treatment
- Patients who did not receive at least one dose of study treatment
- Patients with known vital status at Week 8
 - Dead prior to opening of projected Week 8 visit window
 - Completed Week 8 visit after opening of projected Week 8 visit window
 - Any visit/contact with visit date after opening of projected Week 8 visit window
 - Vital status recorded with last known alive date after opening of projected Week 8 visit window
- Patients with unknown vital status at Week 8
 - Lost to follow-up prior to opening of projected Week 8 visit window
 - Withdrawal of informed consent to any follow-up prior to opening of projected Week 8 visit window

The following categories will be summarized at Week 12 by treatment group, open-label and pooled sacubitril/valsartan:

- Patients who received at least one dose of studytreatment
- Patients who did not receive at least one dose of study treatment
- Patients with known vital status at Week 12
 - \circ Dead
 - o Visit
 - In person with patient
 - Telephone (or video) contact with patient
 - Known alive through other contact with patient or contact with party other than patient
 - Other contact with patient (mail, email, text, social media, etc.)
- Patients with unknown vital status at Week 12
 - o Lost to follow-up
 - Withdrawal of informed consent to any follow-up

Additionally, listings of inclusion/exclusion criteria, screening disposition, reason for withdrawal of consent and study treatment disposition will be provided.

Any visit that did not occur per protocol will be listed with the reason it was not done.

2.3.2 **Protocol deviations**

The number and percentages of protocol deviations by category will be summarized by study phase (see Section 2.1.1 for study phase definitions). Additionally, a listing of protocol deviations during the study will also be presented. The RS will be used.

2.3.3 Index hospitalization

The number and percentages of the following information about patients and their index hospitalization visit will be summarized by treatment group. The RS will be used.

- Patient in shock (No, Yes, Unknown)
- Patients receiving following treatment from index hospitalization to randomization
 - Vasopressor (No, Yes, Unknown)
 - Inotrope (No, Yes, Unknown)
 - Nitroprusside (No, Yes, Unknown)
 - Nesiritide (No, Yes, Unknown)
 - Patient cared for in Intensive Care Unit (ICU) (No, Yes, Unknown)

The number and percentage (categorical variables) and descriptive statistics (continuous data) for information on patient index hospitalization discharge will be summarized by treatment group. The RS will be used.

- Duration of index hospitalization stay in days [(*date:time of discharge date:time of arrival*)/(3600*24)]
- Discharge disposition (Home or with family/friends, Rehabilitation facility, Skilled nursing facility, Death, Unknown)
- Discharge weight (kg)
- New York Heart Association (NYHA) class (I, II, III, IV, Not done)
- Patient experienced worsening heart failure since randomization (No, Yes, Unknown)
- Patient cared for in ICU (No, Yes, Unknown)
 - Number of nights in ICU since randomization
- Patient treated with any of the following medication classes since randomization (Intravenous inotrope, Intravenous vasopressor, Nitroprusside, No, Unknown)
- Patient took third dose of double-blind study treatment (No, Yes)

All information relating to the index hospitalization will be listed.

2.3.4 Demographics and other baseline characteristics

Demographics, baseline characteristics, and disease history are collected at the screening visit. Descriptive summaries and/or listings will be provided. The number and percentage (categorical variables) and descriptive statistics (continuous data) for the information below will be summarized by treatment group for both double-blind and open-label patients.

The FAS will be used.

Demographics and baseline characteristics

Demographic variables include:

- Age (years), age group (<65 years and \geq 65 years; <75 years and \geq 75 years)
- Sex (Male, Female)
 - Child bearing status (Able to bear children, Premenarche, Post-menopausal [perprotocol >12 months], Sterile-of child bearing age)
- Race (Caucasian, Black, Asian, Native American, Pacific Islander, Unknown, Other)
- Ethnicity (Hispanic or Latino, Not Hispanic or Latino)
- Source of patient referral (Physician's own practice, Physician referral, Advocacy group, ER or hospital, Friend/family member, Patient database, Unknown, Other)

Baseline characteristic variables include:

- Height (cm)
- Weight (kg)
- Body mass index (BMI) (kg/m^2) [= weight (kg)/height (m)² from screening visit 1]
 - BMI categories (<20, 20 <25, 25 30, >30 kg/m²)
- Smoking history (Former, Current, Never)
- Heart rate (bpm)
- Bundle branch block (or Intraventricular Conduction Delay [IVCD]) present (No, Yes)
 - Bundle branch block type (Left bundle branch [LBB] block, Right bundle branch [RBB block], Non-specific intraventricular conduction delay)
- NT-proBNP (pg/mL), separately for values based on clinical laboratory samples processed and assessed by the central and local laboratories
 - NT-proBNP categories (<450, 450 <900, 900 <1600, 1600 <3200, 3200 <7400, 7400 <10000, ≥10000 pg/mL)
- BNP (pg/mL), separately for values based on clinical laboratory samples processed and assessed by the central and local laboratories
 - O BNP categories (<100, 100 <225, 225 <400, 400 <800, 800 <1850, 1850 <2500, ≥2500 pg/mL)

Disease characteristics

Disease characteristic variables include:

- Category of prior chronic heart failure (CHF) medication (ACEi, Angiotensin Receptor Blocker [ARB], Beta blocker, Aldosterone antagonist, Ivabradine, Hydralazine, Nitrates [long lasting], Digoxin, Diuretic)
- ACEi naïve (No, Yes); ARB naïve (No, Yes); ACEi/ARB naïve (No, Yes)
- History of HF prior to qualifying HF event (No, Yes, Unknown)
- Number of hospitalizations with primary diagnosis of HF within past 12 months not including index hospitalization
 - Number of hospitalizations categories $(0, 1, 2, \ge 3, \text{Not Applicable})$
- Total number of hospitalizations for any reason within past 12 months
- NYHA classification 30 days prior to index hospitalization (I, II, III, IV, Unknown)
- Ejection fraction (%)
 - Ejection fraction categories (>40%, >30% 40%, >20% 30%, ≤20%)
- Time from presentation to randomization (days)

Cardiovascular history

Cardiovascular history will be summarized. The following disease information will be collected:

- Hypertension (No, Yes, Unknown)
- Transient Ischemic Attack (TIA) (No, Yes, Unknown)
- Stroke (No, Yes, Unknown)
- Peripheral vascular disease (No, Yes, Unknown)
- Chronic renal insufficiency [eGFR <60 ml/min/1.73m² on testing >30 days prior to index hospitalization] (No, Yes, Unknown)
 - Chronic Kidney Disease (CKD) stage (CKD stage 3 [eGFR 30 59], CKD stage 4 [eGFR 15 29], CKD stage 5 [eGFR <15 or dialysis])
- Arrhythmia (No, Yes, Unknown)
 - Arrhythmia type (Atrial fibrillation, Atrial flutter, Supraventricular tachycardia, Ventricular tachycardia)
- Pacemaker/Implantable Cardioverter Defibrillator (ICD) (No, Yes, Unknown)
 - Device type (Pacemaker [conventional], Cardiac resynchronization therapy no ICD [CRT-P], Cardiac resynchronization therapy – with ICD [CRT-D], ICD only [single/dual], Other, Unknown)
- Moderate to severe valvular heart disease (No, Yes, Unknown)
 - Heart disease type (Mitral regurgitation, Aortic regurgitation, Aortic stenosis, Tricuspid regurgitation)
- Prior valvular heart surgery (No, Yes, Unknown)

• Valvular surgery type (Mitral, Aortic, Tricuspid, Pulmonic)

Non-Cardiovascular Medical History

Non-cardiovascular medical history and ongoing conditions will be summarized and listed. The summaries will be presented by primary system organ class (SOC), preferred term (PT) and treatment group for both double-blind and open-label patients. Non-cardiovascular medical history and ongoing conditions will be coded using Medical Dictionary for Regulatory Activities (MedDRA) terminology (v19.0 or later).

Surgeries and Medical Procedures

Surgeries and medical procedures will be listed, including the reason, start date and end date. Surgeries and medical procedures will be coded using MedDRA terminology (v19.0 or later).

2.4 Treatments (study treatment, rescue medication, concomitant therapies, compliance)

The SS will be used for all analyses associated with study treatment and medications, unless otherwise specified.

2.4.1 Study treatment / compliance

The duration of double-blind study treatment phase is defined as:

Duration (days) = (date of last study treatment in double-blind study phase - date of first study treatment) +1

The first date of study treatment is recorded on the Dose Administration (Visit 2) eCRF.

The duration of the open-label study treatment phase is defined as:

Duration (days) = (date of last study treatment in open-label study phase - date of first study treatment in open-label phase) +1

The duration of the pooled phase (sacubitril/valsartan in double-blind phase and/or sacubitril/valsartan in open-label phase) is defined as:

Duration (days) = (date of last study treatment of sacubitril/valsartan [any phase] - date of first study treatment of sacubitril/valsartan [any phase]) +1

Summary statistics will be displayed for the duration of double-blind study treatment, duration of open-label study treatment and duration of pooled sacubitril/valsartan by phase.

The durations will also be categorized into weekly time intervals (<7 days, 7 - <14 days, 14 - <21 days, ..., etc.). The number and percentage of patients in each category will be presented by phase.

Total patient-days of exposure will also be summarized by phase.

In addition, the number and percentages of each dose level dispensed by visit will be summarized by treatment group and open-label sacubitril/valsartan. The number and percentage of the maximum dose levels dispensed will also be presented by treatment group and open-label sacubitril/valsartan. Similarly, the up-titrated doses, down-titrated doses and unchanged doses will be summarized by visit, treatment group and open-label sacubitril/valsartan. The number and percentage of patients who were dispensed dose level 3 by Week 6 will be summarized by treatment group.

An additional summary of patient dose level and titration data will be generated by visit and systolic blood pressure using the visit-specific systolic blood pressure cut-off values from the dose titration schedule.

All information on dose administration will be listed.

2.4.2 **Prior**, concomitant and post therapies

Non-HF Medications

Prior and concomitant non-HF medications will be coded according to the World Health Organization (WHO) Drug Reference List (v15.3 or later). Prior and concomitant medications are mutually exclusive, as defined below:

- Prior medications are defined as any medication with an end date prior to the first dose of study treatment
- Concomitant medications are defined as any medications taken on or after the start of study treatment. Prior medications that are 'ongoing' at the time of the first study treatment or whose end date is after first study treatment will be considered a concomitant medication

The number and percentage of patients with concomitant medications that started after study treatment will be summarized by Anatomical Therapeutic Chemical (ATC) class, preferred term and study phase (refer to Section 2.1.1 for study phase definitions). All medications will be listed.

HF Medications

Medication names are provided for ACEi, ARB, beta blocker and other antiplatelets and will be coded using the WHO Drug Reference List (v15.3 or later) and the preferred term will be displayed for these categories.

The number and percentages of prior HF medications at screening will be summarized by treatment group, open-label and pooled sacubitril/valsartan. Similarly, the HF medications collected at randomization will be summarized by treatment group, open-label and pooled sacubitril/valsartan. A descriptive summary for the total daily dose of each medication (for which doses are collected) will also be presented. These summaries will also be presented using the FAS.

The number and percentages of HF medications collected post randomization will be summarized by study phase (see Section 2.1.1 for study phase definitions). The overall summary will be presented. The following medications will be summarized: Beta blocker, Ivabradine, Hydralazine, Nitrites (long acting), Calcium channel blocker, Potassium, Digoxin, Statin, Furosemide, Torsemide, Bumetanide, Hydrochlorothiazide (HCTZ), Diuril (chlorothiazide), Metolazone, Spironolactone and Eplerenone.

Additionally, a descriptive summary for the total daily dose of each diuretic taken post randomization will be presented by visit, treatment group and open-label sacubitril/valsartan;

Novartis	For business use only	Page 26
SAP Amendment 1		CLCZ696BUS01

these include: Furosemide, Torsemide, Bumetanide, HCTZ, Diuril (chlorothiazide), Metolazone, Spironolactone and Eplerenone.

HF Medications at Index Hospitalization Discharge

The number and percentages of HF medications at the index hospitalization discharge will be summarized by treatment group, open-label and pooled sacubitril/valsartan. The following medications will be summarized: Beta blocker, Ivabradine, Hydralazine, Nitrites (long acting), Calcium channel blocker, Potassium, Digoxin and Statin. Additionally, the number and percentages of each daily diuretic and/or potassium taking during the index hospitalization collected at discharge, the route (when applicable) and total daily dose will be summarized by treatment group, open-label and pooled sacubitril/valsartan.

These summaries will also be presented using the FAS.

Post Randomization Non-study Drug ACEi/ARB

Any ACEi and/or ARB taken after randomization will be listed.

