	Patients will be randomized to sacubitril/valsartan or enalapril. All patients randomized to sacubitril/valsartan will require a 36-hour wash-out from previous ACEi treatment prior to first dose of active study treatment. All randomized patients in the trial will remain hospitalized for observation for 6 hours following the third dose of study medication. See section 3.1 for more details.
	At the end of the 8-week treatment period, all patients will enter a 4 -week follow up period on open label sacubitril/valsartan.
Population	The study population will consist of male and female patients, ≥ 18 years of age, admitted to hospital for acute decompensated heart failure. The goal is to randomize a total of approximately 882 patients to sacubitril/valsartan or

 enalapril in a 1:1 ratio in approximately 170 centers in the United States. At the time of randomization, patients will have been stabilized, defined for this study as: SBP ≥100mm Hg for the preceding 6 hours prior to randomization; no symptomatic hypotension No increase (intensification) in i.v. diuretic dose within last 6 hours prior to randomization No i.v. inotropic drugs for 24 hours prior to randomization No i.v. vasodilators including nitrates within last 6 hours prior to randomization; 		
Patients eligible for inclusion in this study have to fulfill all of the following criteria:1. Possess the capacity to provide written informed consent which must be obtained before any assessment is performed.		
2. Patients \geq 18 years of age, male or female.		
 Currently hospitalized for ADHF. Patients with a diagnosis of acute heart failure had to have symptoms and signs of fluid overload (i.e. jugular venous distention, edema or rales on auscultation or pulmonary congestion on chest x-ray) at time of hospitalization. 		
 4. Eligible patients will be randomized no earlier than 24 hours and up to ten days after presentation while still hospitalized as long as meet the following definition of stable status: □ SBP ≥100mm Hg for the preceding 6 hours prior to randomization; no symptomatic hypotension 		
 No increase (intensification) in i.v. diuretic dose within last 6 hours prior to randomization 		
No i.v. inotropic drugs for 24 hours prior to randomization		
No i.v. vasodilators including nitrates within last 6 hours prior to randomization		

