5.5.5 Permitted dose adjustments and interruptions of study treatment

Every attempt should be made to maintain patients on the target study drug dose level for as long a duration as possible throughout the study. If, however, in the opinion of the investigator, a patient is unable to tolerate the protocol-specified target dose, the investigator should consider whether dose adjustments of concomitant medications may rectify the situation before reducing the dose of study treatment. If adjustment of the concomitant medications is not possible or does not alleviate the side effects of concern, the investigator may down-titrate the dose of the study drug to the previous dose level. If needed, the study drug may be stopped completely, but the patient should continue to attend the study visits and be followed until the completion of the study. Patients may restart their current dose of study drug following an interruption of treatment, based on investigator judgment.

Study drug dose level adjustments should be mainly based on overall safety and tolerability with special focus on hyperkalemia, symptomatic hypotension

Adjustment of study drug dose level

If necessary, the patient may be down-titrated to the next lower dose level. The patient may continue receiving the lower dose level for a recommended period of 1 to a maximum of 4 weeks. Re-challenge to titrate back up to the target dose level should be attempted at 2 weeks. It must be noted that the desired dose of study medication is the highest dose (dose level #3), but patient tolerability and safety must be taken into account.

If the tolerability issues are not alleviated despite down -titration by one dose level, the investigator may lower the study drug dose further to the next lower level for 1 to a maximum of 4 weeks, up to temporary withdrawal of the study drug. Again, once stable, the patient should be re-challenged with up-titration to the next higher dose level in an attempt to bring back the patient gradually to the target study drug dose level (dose level #3). The investigator may choose the next dose level for down - or up-titration according to his or her clinical judgment. The IWRS should be contacted to register any changes in the patient's study drug dose level, including in cases of temporary and permanent withdrawal of the study drug, and to obtain the medication numbers of the study drug supplies required for the new study drug dose level.

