2.1.1 General definitions

Study treatment

Patients will receive either sacubitril/valsartan or enalapril during the first 8 weeks of the study. Study treatment will refer to either of these two drugs.

Baseline

For safety labs and biomarkers, baseline is defined as the last non-missing assessment collected <3 hours from the first dose of study treatment, including matching placebos. For patients not treated, baseline is defined as the last non-missing assessment prior to or on the date of randomization. BNP and NT-proBNP values will be based on clinical laboratory samples processed and assessed by the central laboratory.

For other assessments, including those for which assessment time is collected (ECGs, HF Signs and Symptoms, and pregnancy tests), baseline is defined as the last non-missing assessment prior to or on the start date of study treatment (randomization date for patients not treated), including matching placebos.

Date of first administration of study treatment

Double-blind phase: The date of first administration of study treatment in the double-blind phase is defined as the first date a dose of study treatment is administered and recorded on the Dose Administration (Visit 2) electronic case report form (eCRF).

Open-label phase: The date of first administration of study treatment in the open-label phase is defined as the first date a dose of sacubitril/valsartan is administered in the open-label phase and recorded on the Dose Administration (Visit 7) eCRF.

Pooled phase: The date of first administration of study treatment in the pooled phase is defined as the first date a dose of sacubitril/valsartan is administered either in the double-blind phase or open-label phase.

Date of last administration of study treatment

Double-blind phase: The date of last administration of study treatment in the double-blind phase is defined as the last date a dose of study treatment is administered in the double-blind phase and recorded on the Dose Administration (Visit 7) eCRF, or earlier if prematurely discontinued and recorded on the Early Investigational Product Permanent Discontinuation eCRF.

Open-label phase: The date of last administration of study treatment in the open-label phase is defined as the last date of sacubitril/valsartan is administered in the open-label phase and recorded on the Drug Administration eCRF.

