Pooled phase: The date of last administration of study treatment in the pooled phase is defined as the last date of sacubitril/valsartan administered either in double-blind phase or open-label phase.

Study day

The study day describes the day of the assessment relative to the date of randomization.

The study day will be calculated as the difference between the date of assessment and the date of randomization plus 1. If the date of assessment is prior to the date of randomization, the study day will be negative and will be calculated as the difference between the date of the assessment and the date of randomization.

Double-blind phase

Assessments performed at Weeks 1, 2, 4, 6, or 8 (including, but not limited to, vital signs) are assigned to the double-blind phase for summarization purposes. Unscheduled assessments are not assigned to a study phase for purposes of by-visit summaries.

For summarization of adverse events [AEs], medications, protocol deviations, notable vital signs and laboratory abnormalities, and symptomatic hypotension by study phase, an assessment during the double-blind phase is defined as any assessment obtained in the following time interval:

Date of randomization (or date of first administration of study treatment, as appropriate) through the date of the Week 8 visit, inclusive. For patients without a Week 8 visit, a projected Week 8 visit date will be derived relative to their randomization date.

An 'active treatment' assessment is defined for sensitivity analyses starting with the first dose of study treatment in patients randomized to enalapril and the third dose of study treatment in patients randomized to sacubitril/valsartan.

Open-label phase

Assessments performed at Weeks 10 or 12 (including, but not limited to, vital signs) are assigned to the open-label phase for summarization purposes. Unscheduled assessments are not assigned to a study phase for purposes of by-visit summaries.

For summarization of AEs, medications, protocol deviations, notable vital signs and laboratory abnormalities, and symptomatic hypotension by study phase, an assessment during the open-label phase is defined as any assessment obtained in the following time interval:

After the date of the Week 8 visit. For patients without a Week 8 visit, a projected Week 8 visit date will be derived relative to their randomization date.

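### Pooled sacubitril/valsartan duration counts off-drug days between phases as exposure when a patient stops blinded drug early and later starts open label

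*SAP*

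**What the plan says.** SAP 2.4.1 gives three durations, each a last date minus a first date plus 1:

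- Double-blind: "date of last study treatment in double-blind study phase - date of first study treatment".
- Open label: "date of last study treatment in open-label study phase - date of first study treatment in open-label phase".
- Pooled: "date of last study treatment of sacubitril/valsartan [any phase] - date of first study treatment of sacubitril/valsartan [any phase".

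SAP 2.1.1 defines the pooled dates to match. The start is the "first date a dose of sacubitril/valsartan is administered either in the double-blind phase or open-label phase" and the end is the "last date of sacubitril/valsartan administered either in double-blind phase or open-label phase". For an early stopper, the same section ends double-blind treatment at the discontinuation date, so the double-blind duration stops when the drug does.

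SAP 2.4.1 applies the durations to summary statistics and weekly categories, and adds: "Total patient-days of exposure will also be summarized by phase". It gives no separate derivation for patient-days.

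On early stopping, Protocol 5.5.5 says: "If needed, the study drug may be stopped completely, but the patient should continue to attend the study visits". On entry to open label, the Protocol summary (Study design) says: "At the end of the 8-week treatment period, all patients will enter" the open-label follow-up. Protocol 5.5.4 is narrower and sends on those who complete 8 weeks of treatment. The open-label phase definition in SAP 2.1.1 leaves out only patients who died, withdrew consent or were lost by the projected Week 8 date.

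**The concern.** The double-blind and open-label durations each stop and start with dosing, so neither contains the interval between phases. The pooled duration uses only the outer two dates and therefore does contain it. If that interval includes days without drug, the pooled figure is no longer the sum of its parts, and nothing in the SAP corrects it.

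The error can only go upward, and it is largest in patients who stopped blinded drug soonest. Protocol 5.5.6 also lets a patient who is off study drug take a non-study ACE inhibitor or ARB. Some of the days counted as sacubitril/valsartan exposure could therefore be days on another drug. At stake are the pooled duration statistics, the weekly categories and pooled patient-days.

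**Working it through.** The documents state no exposure or patient-day figure, so there is none to reproduce. The check is date arithmetic on the SAP's formulas.

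**Inputs.** Day 1 (randomization), day 56 (Week 8 visit) and day 84 (last open-label visit) come from Protocol Table 6-1. Protocol 3.1 and 5.5.4 and SAP 1.1 put the last blinded dose on the morning of the Week 8 visit and the first open-label dose on the evening of the next day, so days 56 and 57. The sacubitril/valsartan arm has about 882 / 2 = 441 patients.

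**Per patient.** With the same start date in both calculations:

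excess = pooled − (double-blind + open label) = open-label start − last blinded dose − 1

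With open label on days 57 to 84 (84 − 57 + 1 = 28 days) and pooled duration 84 − 1 + 1 = 84:

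| Last blinded dose | Double-blind | Open label | Sum | Pooled | Excess |
|---|---|---|---|---|---|
| Day 56 (planned) | 56 | 28 | 84 | 84 | 0 |
| Day 55 (Table 6-1 footnote) | 55 | 28 | 83 | 84 | 1 (1.2%) |
| Day 42 | 42 | 28 | 70 | 84 | 14 (20%) |
| Day 28 | 28 | 28 | 56 | 84 | 28 (50%) |
| Day 14 | 14 | 28 | 42 | 84 | 42 (100%) |

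In the day-28 row, the patient moves from the weekly category that starts at 56 days (8 weeks) to the one that starts at 84 days (12 weeks).

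**Enalapril arm.** The first sacubitril/valsartan date falls in the open-label phase, so no between-phase gap can arise. These patients still add to pooled exposure: 441 × 28 = 12,348 days if all complete open label.

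**Whole study.** Let f be the share of the 441 who stop on day 28 and start open label on day 57. The documents do not give f. All other patients are taken to follow the planned schedule.

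- Excess = 441 × f × 28
- Correct total = 441 × [(1 − f) × 84 + f × 56] + 12,348

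| f | Excess days | Correct total | Overstatement |
|---|---|---|---|
| 0 | 0 | 49,392 | 0 |
| 5% | 617 | 48,775 | 1.3% |
| 10% | 1,235 | 48,157 | 2.6% |
| 20% | 2,470 | 46,922 | 5.3% |

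The stopping day matters too. At f = 10%, a stop on day 42 gives 1.3% and a stop on day 14 gives 3.9%.

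**Footnote reading.** If all 441 skipped study drug on the Week 8 visit day and nobody stopped early, the excess would be 441 days over 441 × 83 + 12,348 = 48,951, or 0.9%.

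**The case against.** The strongest reply is that the affected group may be small or empty. On the Protocol 5.5.4 wording, only patients who complete 8 weeks of treatment go on to open label. Protocol 5.5.5 keeps early stoppers in visits without saying that they receive open-label drug, and the SAP 2.1.1 phase definition classifies assessments, not dosing. This stands as a limit on the size. It does not remove the point, because the Protocol summary sends all patients to open label and Protocol 3.2 presents that period as an opportunity for every patient. The formula has to work under either wording.

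A second reply is that last minus first plus 1 is an ordinary convention. All three durations count interruptions within a phase, and the proposed sum would still do so. That is true, but the present point is narrower: the pooled figure can disagree with the SAP's own two components.

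Three stronger readings are tempting, and the documents support none of them:

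- *The 36-hour washout inflates every patient's duration.* On the planned schedule, the last blinded and first open-label doses fall on consecutive calendar dates, so no whole day is added. Only the Table 6-1 footnote, which has patients omit study drug on the visit day, would add one.
- *Placebo days are counted because the first two doses in this arm are placebo.* The pooled start in SAP 2.1.1 is a date on which sacubitril/valsartan is given, which can be read as the first active dose. For the double-blind phase, counting from first rather than first active treatment is a choice recorded in the SAP document history.
- *Event rates per patient-day will be too low.* The SAP text specifies no such rate. Adverse events are summarized as numbers and percentages of patients.

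**Conclusion.** The pooled formula is wrong as written for one group: patients randomized to sacubitril/valsartan who stop blinded drug early and later start open label. For a last blinded dose on day 28 and open label on days 57 to 84, it reports 84 days instead of 56 (+50%).

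Across the study, pooled patient-days are overstated by about 1.3% to 5.3% if 5% to 20% of that arm follow this pattern. This assumes that patient-days are the sum of the durations, that everyone else follows the planned schedule, and that all enalapril patients contribute 28 open-label days. If no early stopper starts open label and the planned schedule is followed, the overstatement is zero. The true share cannot be determined from the documents.

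The point is minor. It touches a descriptive exposure summary only. No hypothesis test uses pooled duration, and the primary analysis is unaffected. The double-blind and open-label durations do not contain this gap and are still reported separately.

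**What to change.** In SAP 2.4.1, define pooled duration as the double-blind duration (patients randomized to sacubitril/valsartan only, as already defined) plus the open-label duration. For enalapril-randomized patients it is the open-label duration alone. State that this sum is used for the pooled summary statistics, weekly categories and patient-days.

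The cost is one formula. Both components already exist, no new data are needed, and patients on the planned schedule stay at 84 days. Interruptions within a phase remain counted, as they are now.

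Two sets of passages should also be reconciled, because they determine how large the gap can be:

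- the Table 6-1 footnote on dosing on the Week 8 visit day, against Protocol 3.1, Protocol 5.5.4 and SAP 1.1;
- the Protocol summary against Protocol 5.5.4, on who enters open label.
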